5.1 Overall design

5.1.1 Study Hypotheses

- (1) The physical activity of most children with cancer does not meet the guidelines suggest that their physical activity is positively related to self-efficacy, enjoyment, family support and the physical activity of their parents;
- (2) Compared with the control group, parent-child activity intervention can improve the physical activity of children with cancer and their parents, promote the self-efficacy and physical enjoyment of physical activity, and enhance the family support of children.

5.1.2 Study design

This study is a class of experimental study. The pediatric malignant tumor patients and

the parents were selected by convenience sampling.

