4.1.2 Exclusion criteria

Children with physical impairment, cognitive impairment, or impaired mental status are excluded.

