4.2.2 Exclusion criteria

Parents with emotional or psychiatric disorders and cognitive problems are excluded.

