5.2 Study design process

Establish an intervention team composed of researchers and qualified doctors and nurses, and evaluate the intervention members. Study subjects were recruited according to the exclusion criteria, and after obtaining informed consent and signing the consent form, the study subjects were included in the control group and experimental group. In order to prevent contamination, it was divided into control group and experimental group according to the chronological order, that is, the experimental group was included first, and in the experimental group, the control group was included after the sample size is sufficient. The control and experimental groups received usual care and parent-child activity intervention. Data were collected and analyzed at enrollment (T0), 1 month (T1), 2 months (T2), 3 months (T3), and 3 months (T4) after the intervention.

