5.3 Methods to reduce the bias

- (1) Adopt the research method of similar experiment, collect all the data of the experimental group, and then recruit the control group to collect the data to avoid the occurrence of contamination;
- (2) The intervention team members shall receive unified physical activity training and assessment before the intervention, jointly propose the possible situation during the implementation of the intervention, unify the interpretation method of the questionnaire items, and give unified language answers to the questions about the questionnaire;

(3) In the process of collecting the questionnaire, collect the questionnaire on the spot, evaluate and check the completion of the questionnaire, timely find and correct the missing contents, ensure the integrity and effectiveness of the questionnaire information, and timely input the data after collecting the questionnaire;

(4) When analyzing the data, check the integrity and validity of the data again, and make remedial plan for the incomplete questionnaire; establish a database, and two people jointly input and check the data to ensure the accuracy of data entry.

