5.4.2 Statistical Analysis

The Epidata3.1 database was established, the data was entered by two people, and the SPSS25.0 statistical software was used for statistical analysis, and the test level was set at $\alpha = 0.05$.

(1) Description statistics: ① Data following normal distribution are described by mean and standard deviation; ② data without normal distribution are described by median and interquartile spacing.

(2) Data analysis: (3) Use Excel to establish the database, double input data, and use SPSS25.0 statistical software for statistical analysis, as follows:

① Using frequency, composition ratio, mean, standard deviation to describe the general data of children with tumors and their parents, the disease data of children and other conditions;

② The t-test, chi-square test or rank sum test were balanced for general data, physical activity, physical activity self-efficacy, physical activity enjoyment, and physical activity social support between the experimental and control groups.

③ One-way repeated measures analysis of variance was used to compare the number of high intensity physical activity minutes between children and parents in the experimental group.

④ If the data of physical activity, physical activity self-efficacy, physical activity enjoyment and physical activity social support meet the normal distribution (Shapiro-Wilk test) and equal variance (scatter plot), the mixed design analysis of variance shall be used to intervene the effects of main effect, time main effect, intervention time effect and confounding factors; if not satisfied, the generalized

estimation equation is used.

6. Research intervention

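### Convenience sampling in two calendar phases whose group is known in advance leaves room for selection to differ between groups, and the plan neither prevents nor records it

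*Combined protocol and SAP*

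**What the plan says.** - **Sampling.** Section 5.1.2: the patients and "the parents were selected by convenience sampling". Section 4.4 locates recruitment among inpatients of one paediatric unit. No rule requires every eligible family to be approached.
- **Allocation.** Section 5.2 assigns groups by calendar order: "the experimental group was included first, and in the experimental group, the control group was included after the sample size is sufficient". Section 5.3, item 1, gives the reason and confirms the separation: "collect all the data of the experimental group, and then recruit the control group to collect the data to avoid the occurrence of contamination".
- **Exclusions.** Section 4.1.2: "Children with physical impairment, cognitive impairment, or impaired mental status are excluded". Section 4.2.2: "Parents with emotional or psychiatric disorders and cognitive problems are excluded". Neither names an instrument, a grade or a threshold.
- **Bias control.** Section 5.3 deals with contamination, team training, questionnaire completeness and data entry. It does not deal with who is approached, excluded or refuses.
- **Partial safeguards.** Section 7 collects the child's activity, self-efficacy, enjoyment and family support, and the parents' activity, at T0. Section 5.4.2 plans baseline tests between the groups. It also plans a mixed-design ANOVA (otherwise GEE) with group, time, group-by-time and confounders that it does not name.

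**The concern.** Three features combine: freedom over whom to approach, exclusion terms left to judgement, and a group that is known before the approach. The two phases also ask different things of a family. The programme needs families who will attend group games and log activity every week (6.1, 6.2); the control phase does not. The same recruiter could, without any intent, approach or exclude differently in the two phases.

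The exclusion for physical impairment bears directly on the primary outcome. If keener or fitter families are over-represented in one phase, the groups differ in activity for reasons unrelated to the programme. Without a record of who was passed over, the report cannot show whether this happened.

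**Working it through.** The plan gives no figure for selection, so the check asks how large a false-positive rate a given selection shift would produce under each analysis that 5.4.2 could support.

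**Inputs**
- n = 27 per group (5.4.1: 21/0.8 = 26.25, rounded up). The figure of 20.8621 behind it does not follow from the printed formula. With difference 130.31, average-variance SD √((50.39² + 116.92²)/2) = 90.03, two-sided 0.05 and 90% power, the formula gives 10.03. That is a separate matter and nothing below depends on it.
- Test level 0.05 (5.4.1), taken as two-sided because the plan does not say.
- Control SD 50.39 minutes (5.4.1). With no true effect this is the natural scale, because 90.03 averages in the experimental-group SD. Shifts in minutes: 0.3 × 50.39 = 15 and 0.5 × 50.39 = 25.
- Assumed, not in the documents: selection shift b = 0.3 or 0.5 SD; T0-to-follow-up correlation ρ = 0.3 to 0.7; zero true effect; normal data with equal SDs; one follow-up time.

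**Step 1. T0 ignored.** Noncentral t with 52 df, critical value 2.007, noncentrality b√(n/2).
- b = 0.3: 0.3 × √13.5 = 1.102, rejection 19.1%.
- b = 0.5: 0.5 × √13.5 = 1.837, rejection 43.8%.
- With 21 per group: 15.8% and 35.3%.

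**Step 2. Linear adjustment for T0, shift equally present at T0 and follow-up.** The expected remaining difference is b(1 − ρ) and the residual SD is √(1 − ρ²). For b = 0.3 and ρ = 0.5, the noncentrality is about 0.15/(√(2/27) × 0.866) = 0.64. Simulation of 200,000 trials per cell, 27 per group:

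| ρ | b = 0.3 | b = 0.5 |
|---|---|---|
| 0.3 | 12.2% | 24.5% |
| 0.5 | 9.3% | 17.1% |
| 0.7 | 7.2% | 11.3% |

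**Step 3. Change from T0 (the two-time form of group-by-time), same constant shift.** The shift cancels, b − b = 0. Simulated rejection is about 5% in every cell.

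**Step 4. Change from T0, shift absent at T0 and present at follow-up (keener families rise more steeply).** The SD of the change is √(2(1 − ρ)), which equals 1 at ρ = 0.5. The test is then the same as in step 1: 19.1% and 43.8%.

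**Step 5. The baseline tests as reassurance.** Section 5.4.2 plans them: "The t-test, chi-square test or rank sum test were balanced for general data, physical activity, physical activity self-efficacy, physical activity enjoyment". With 27 per group, a t-test has 80% power only for a true shift of about 0.78 SD (0.78 × 50.39 = 39 minutes). An observed difference of 2.007 × √(2/27) = 0.55 SD (about 28 minutes) already reaches p = 0.05. A non-significant baseline test therefore does not exclude a shift large enough to matter.

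**The case against.** The strongest reply is that the plan measures much of what selection would act on. T0 activity is the primary outcome itself, and self-efficacy, enjoyment, family support and parental activity are close proxies for keenness. A group-by-time test removes any constant difference (step 3). This stands, and it rules out the reading that motivation goes wholly unrecorded. It does not close the gap. The confounders are unnamed, fitness is not tested directly, the group main effect is listed beside group-by-time and does not cancel even a constant shift, and group-by-time does not cancel a steeper rise in keener families (step 4).

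A reader might also infer that staff could steer a family into one arm or the other. The documents do not support that, because the groups are never open together. The possible route is selective approach or exclusion within a phase.

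Nor do the documents say who screens. Section 5.2 says only "Establish an intervention team composed of researchers and qualified doctors and nurses", so knowledge of the open group is inferred from the fixed order. Convenience sampling does not by itself mean hand-picking, though nothing rules it out.

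The direction is not certain either. Control families must also accept five assessments, which may select committed families too.

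**Conclusion.** The concern holds as a risk that the plan leaves open, not as evidence that selection took place. Convenience sampling, non-overlapping phases with a known group, and exclusions without an operational definition allow selection to differ between phases, and no record would reveal it. Bias toward the programme is plausible but not established.

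The size depends on an assumed shift and on the analysis used. A reader might take 19% and 44% as the error rates of this trial. They apply only if T0 is ignored, or if the shift appears after T0 (exactly so for a change comparison at ρ = 0.5). If the shift is constant, T0 adjustment brings them to about 7–12% and 11–25%, and a change comparison to about 5%. All figures assume normal data. The planning control SD (50.39) exceeds its mean (35.88), which suggests skewed minutes, so they are illustrations rather than predictions.

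**What to change.** The sequential design and its protection against contamination can stay.

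1. In 5.1.2, replace convenience sampling by consecutive approach: every family on the unit that meets 4.1 and 4.2, in order of admission, with the same script in both phases.
2. Apply the existing exclusions in 4.1.2 and 4.2.2 by one written, recorded procedure that is identical in both phases, without changing who is eligible. It must work for parents as well as children; the documents describe no medical record for parents to rely on.
3. Keep a log by phase of families eligible, approached, excluded (with reason), refusing and enrolled, and report these rates by group.
4. In 5.4.2, base the between-group conclusion on group-by-time with T0 activity accounted for, and name the confounders in advance.
5. Report the result as a non-randomised comparison whatever the rates show.

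The cost is protocol wording, a short log and slightly slower recruitment, with no extra patients. Consecutive approach does not remove calendar-time differences or differential refusal, but the log makes refusal visible.

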5.2 Study design process

Establish an intervention team composed of researchers and qualified doctors and nurses, and evaluate the intervention members. Study subjects were recruited according to the exclusion criteria, and after obtaining informed consent and signing the consent form, the study subjects were included in the control group and experimental group. In order to prevent contamination, it was divided into control group and experimental group according to the chronological order, that is, the experimental group was included first, and in the experimental group, the control group was included after the sample size is sufficient. The control and experimental groups received usual care and parent-child activity intervention. Data were collected and analyzed at enrollment (T0), 1 month (T1), 2 months (T2), 3 months (T3), and 3 months (T4) after the intervention.

5.3 Methods to reduce the bias

- (1) Adopt the research method of similar experiment, collect all the data of the experimental group, and then recruit the control group to collect the data to avoid the occurrence of contamination;
- (2) The intervention team members shall receive unified physical activity training and assessment before the intervention, jointly propose the possible situation during the implementation of the intervention, unify the interpretation method of the questionnaire items, and give unified language answers to the questions about the questionnaire;

(3) In the process of collecting the questionnaire, collect the questionnaire on the spot, evaluate and check the completion of the questionnaire, timely find and correct the missing contents, ensure the integrity and effectiveness of the questionnaire information, and timely input the data after collecting the questionnaire;

(4) When analyzing the data, check the integrity and validity of the data again, and make remedial plan for the incomplete questionnaire; establish a database, and two people jointly input and check the data to ensure the accuracy of data entry.

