The Effects of Parent-Child Activity Program on Physical Activity of Children With Cancer

March 31, 2024

1. Summary

Study Population: Children diagnosed with malignant tumors aged 6 to 14 years.

Outcome measures: ① Main outcome measures: physical activity behavior in children with cancer; ② secondary outcome indicators: height, weight, BMI, body fat, muscle, self-efficacy of physical activity, physical activity enjoyment, perceived social support in physical activity, and physical activity of parents.

Study Intervention: ① Control group: the children and their parents receive routine care and health education guidance, receive physical activity guidelines and suggestions for patients with malignant tumors provided by the researchers, and issue health knowledge education manual. In addition, the researchers and other members of the intervention team do not provide information about parent-child activities; ② Experimental group: the experimental group receives online and offline family-based parent-child physical activity intervention. It includes participating in offline group parent-child activities during hospitalization, including family competitive games and knowledge contests, etc., popularizing science of physical activity and parent-child sports activities to children and parents regularly after discharge, and pushing tweets, sports and practice videos related to physical activities and parent-child sports activities. Exercise were followed every 4 weeks and assessed for the previous session. The intervention protocol lasts 12 weeks and is followed up 3 months after the intervention is completed.

Sample size: with physical activity as the outcome indicator, the sample content was used to estimate the sample content calculation method, and the test level α was set to

0.05, and the control degree was 90%. According to the results of the literature review, 20.8621 subjects in the experimental group and the control group, considering 20% lost to follow up, so at least 27 subjects in the experimental group and the control group.

2. Introduction

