5.4 Statistical analysis

5.4.1 Sample size

The number of sample cases required for the study was estimated by two sample content calculation using physical activity as the outcome measure. Taking the medium and high intensity physical activity of the study subjects as the observed outcome indicator, according to the results, the mean and standard deviation of physical activity minutes of the control group was 35.88 ± 50.39 , the mean and standard deviation of the experimental group was 166.19 ± 116.92 , and the test level was set at 0.05 and the control was 90%. Calculate the formula according to the sample size:

$$n = \frac{(Z_\alpha + Z_\beta)^2 * 2\sigma^2}{\delta^2}$$

We calculated 20.8621 subjects in the experimental group and the control group, considering 20% lost to follow-up, so $n_1=n_2=21/0.8=26.2527$ cases. At least 27 subjects were needed in the experimental and control groups.

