- ① WeChat group communication, enhance the information interaction and emotional support between peers.
- ② Family competition, improve the role of role model.

III . Strengthen the role of medical staff —— Medical staff support

- ① Information and technical support: medical staff shall provide relevant information, venues and goods to the child and their parents.
- ② Emotional support: When children and parents have problems or emotional needs, intervention team members should provide timely answers and encouragement online; at monthly follow-up, researchers will provide separate face-to-face interviews to help them solve their problems.
- ③ Other support: In the offline activities, the medical staff also actively participate in the demonstration for the children and their parents.

(3) The intervention program lasts for 12 weeks and is follow-up for 3 months after the completion of the intervention.

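### With the arms run in sequence and no blinding or hold on analysis, controls can be selected and questioned, and open analysis choices settled, with experimental results in view

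*Combined protocol and SAP*

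**What the plan says.** **Order of the arms.** Section 5.3 (1) says the team will "collect all the data of the experimental group, and then recruit the control group to collect the data". Section 5.2 says "the experimental group was included first, and in the experimental group, the control group was included after the sample size is sufficient", which does not require experimental follow-up to be finished.

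**Access to the data.** Section 5.3 (3) asks staff to "timely input the data after collecting the questionnaire". Section 5.2 adds: "Data were collected and analyzed at enrollment (T0), 1 month (T1), 2 months (T2), 3 months (T3), and 3 months (T4) after the intervention". Item ③ of 5.4.2 is a repeated-measures analysis confined to the experimental group, so it needs no controls. Blinding of assessors or analysts, an embargo and a data lock are not mentioned.

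**What is left open.** The summary gives "Main outcome measures: physical activity behavior in children with cancer". Section 5.4.1 sizes the study by "Taking the medium and high intensity physical activity of the study subjects as the observed outcome indicator". Item ③ of 5.4.2 uses high-intensity minutes, and item ④ refers to physical activity in general. No visit is named as primary. Item ④ lists group, time and interaction effects without saying which one decides. For gaps in the data, 5.3 (4) says to "make remedial plan for the incomplete questionnaire", and places this at the time of analysis.

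**How controls are found and questioned.** Section 5.1.2 uses convenience sampling. Under section 7 (1), data collectors fill in the questionnaire for participants who cannot do so themselves.

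**The concern.** The sequence is offered as protection against contamination, and it does serve that purpose. It also means that those who recruit controls and collect their self-reported activity may already know the experimental means by visit and intensity, which are the figures the controls will be compared with. That knowledge can influence which families are approached, how their answers are drawn out, and how incomplete forms are scored.

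Separately, the deciding variable, visit and model effect are not fixed, so they too can be settled after the experimental results are known. At stake is a between-group difference that favours the programme for reasons other than its effect, in a non-randomised comparison planned at 27 per group.

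**Working it through.** The plan gives no figure on this point, so the check compares its sections and then illustrates size under stated assumptions.

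**Step 1. How much experimental data exists when controls start.** Section 6.1 states: "The intervention program lasts for 12 weeks and is follow-up for 3 months after the completion of the intervention". That is about 3 + 3 = 6 months per family.
- Under 5.3 (1), the first control enters about 6 months or more after the last experimental enrolment, with all T0–T4 data in hand.
- Under 5.2, the first control could enter straight after the last experimental enrolment, with up to about 6 months of experimental data still to come. Families enrolled earlier would by then have follow-up data entered.

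**Step 2. What the order is responsible for.**

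| Open item | Source | Still open with concurrent arms? |
|---|---|---|
| Activity variable | Summary, 5.4.1, 5.4.2 ③ and ④ | Yes |
| Deciding visit | 5.2 | Yes |
| Deciding model effect | 5.4.2 ④ | Yes |
| Missing-item remedy | 5.3 (4) | Yes |
| Which controls are taken, and how they are questioned, with experimental results known | 5.1.2, 5.3 (1), section 7 (1) | Largely no; this is what the order adds |

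**Step 3. Illustration of the open choices.** Assumptions: no true effect; 21 analysed per group (the plan's 20.8621 rounded up, and close to 27 × 0.8 = 21.6); five visits with equal between-visit correlation of 0.3 to 0.7; change from T0. The variable and visit with the largest experimental mean/SD are chosen first, then tested by a two-sample t-test at two-sided 5%. Three intensity variables correlated 0.5 are also an assumption.
- One variable, four visits: favourable false positives 0.059–0.064, against 0.025 nominal. Counting both tails gives 0.065–0.069, against 0.05.
- Three variables by four visits: favourable 0.110–0.121.
- The same freedom used after both arms are seen: favourable 0.079–0.084 (one variable) and 0.183–0.185 (three).

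Choosing from the experimental arm alone therefore inflates error less than choosing at the end with both arms visible. These rates are evidence about missing pre-specification, not about the sequence.

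**Step 4. Sensitivity for the part specific to the order.** The documents give no size for it, so a range is assumed. If selection or prompting lowers the control mean by s standard deviations and there is no true effect, the two-sided error is approximately Φ(s/√(2/n) − 1.96) + Φ(−s/√(2/n) − 1.96). With n = 21, √(2/21) = 0.309.
- s = 0.1: 0.06
- s = 0.25: s/0.309 = 0.81, so Φ(−1.15) + Φ(−2.77) = 0.125 + 0.003 = 0.13
- s = 0.5: 0.37

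Nothing in the documents shows that any such shift would occur.

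**The case against.** The strongest reply is about attribution. A reader might infer that the order itself raises the false-positive rate to 6% or 12%. It does not: the unnamed variable, visit and missing-item rule would be just as open with concurrent arms, and Step 3 shows more inflation when both arms are seen. The simulated single-visit t-test is also not the planned analysis. Item ④ of 5.4.2 is a mixed-design ANOVA, or GEE, over all visits, and the t-tests in item ② are worded as balance checks. All of this stands, and the rates are kept only as an illustration.

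The plan also has partial safeguards. Eligibility is written down (4.1, 4.2), item explanations and answers to queries are to be uniform (5.3 (2)), instructions are standardised (section 7 (1)), and missing answers are corrected on the spot (5.3 (3)). These narrow the room for steering but do not close it. The criteria are broad, sampling is by convenience, and 5.3 (4) still expects incomplete questionnaires.

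Finally, the wording in 5.2 about analysis at each visit may be only a list of measurement occasions in translated text. It is weak evidence of planned interim analysis. The point does not depend on it, because prompt data entry, the experimental-only item ③ and the absence of any hold are enough to leave the results accessible.

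**Conclusion.** The concern holds as one of opportunity. Unblinded staff can select and question controls knowing the experimental results, and the analysis choices that remain open can be settled at the same stage. Two causes should be kept apart: missing pre-specification leaves the choices open, and the sequence exposes the recruitment and handling of controls. The second cannot be quantified from the documents; Step 4 shows only what assumed shifts would do.

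Two stronger readings are not supported. One is that every experimental result will be in hand before the first control is approached. That is true under 5.3 (1) but not required by 5.2. The other is that choices have been, or will be, made to suit the results; nothing in the documents shows this.

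The point is worth acting on because the change is cheap and specific, not because an error has been demonstrated.

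**What to change.** 1. **Reconcile 5.2 and 5.3 (1)** so that both state one trigger for starting control recruitment.
2. **Pre-specify.** Sign and date an analysis plan before any experimental post-T0 outcome data are summarised, and at the latest before the first control is approached. It should name one primary variable (for example the moderate-to-high intensity minutes used in 5.4.1), one deciding visit or group-by-time contrast within the item ④ model, and the missing-item scoring rule.
3. **Embargo.** In 5.2, state that data are collected at T0–T4 and drop the reference to analysis. In 5.3, hold item ③ of 5.4.2 and all outcome summaries until the last control's T4 is entered. Completeness checks, safety listings and the weekly adherence records of 6.2 stay available.
4. **Control recruitment.** Approach all eligible control families consecutively and keep a screening log with reasons for non-entry.

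The cost is a paragraph or two, a dated sign-off and a log. The contamination safeguard and safety monitoring are untouched. The downside is that experimental-only results are delayed. A limit remains: staff who see weekly records and meet families each month stay unblinded, so the embargo reduces the exposure without removing it.
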